24. PUBLICATION OF RESULTS

Chiesi is entitled to publish and/or present any results of this study at scientific meetings, and to submit the clinical trial data to national and international Regulatory Authorities. Chiesi furthermore reserves the right to use such data for industrial purposes. Investigators will inform Chiesi before using the results of the study for publication or presentation and agree to provide the Sponsor with a copy of the proposed presentation. Data from individual study sites must not be published separately.

Negative as well as positive results should be published or otherwise made publicly available.

 Chiesi	Clinical Study Protocol
Clinical Study Code No.: CUSA-081-HEM-01	Version No.: 8.0
EUDRACT No./IND No.: 2019-002124-32/128551	Date: 21 FEB 2023

## List of Abbreviations

ADaM	Analysis Dataset Model
ADR	Adverse Drug Reaction
AE	Adverse Event
AESI	Adverse Event of Special Interest
BMI	Body Mass Index
ATC	Anatomical Therapeutic Chemical
CI	Confidence Interval
CRBSI	Catheter Related Bloodstream Infection
CSR	Clinical Study Report
CVAD	Central Venous Access Device
DBP	Diastolic Blood Pressure
DMC	Data Monitoring Committee
eCRF	Electronic Case Report Form
FAS	Full Analysis Set
HR	Heart Rate
ICH	International Council for Harmonisation
IRT	Interactive Response Technology
ITT	Intention-to-Treat
K-M Estimate	Kaplan-Meier Estimate
PP	Per-Protocol
PT	Preferred Term
SAE	Serious Adverse Event
SAP	Statistical Analysis Plan
SBP	Systolic Blood Pressure
SD	Standard Deviation
SDTM	Study Data Tabulation Model
SOC	System Organ Class
SS	Safety Set
TEAE	Treatment Emergent Adverse Event
WHO	World Health Organization

### VERSION HISTORY

Version	Date	Change History
1.0	07 Nov 2023	First Version

## 1 Introduction

This document presents the Statistical Analysis Plan (SAP) for Chiesi Farmaceutici S.p.A. protocol CUSA-081-HEM-01: READY 1: A Phase 3, Randomized, Double-Blind, Active and Placebo-Controlled Study on the use of CUSA-081 for Dysfunctional Central Venous Access Devices (CVADs).

This analysis plan is based on the final protocol (version 8.0), dated 21Feb2023 and the final electronic case report form (eCRF) dated 05Apr2022.

The SAP provides the description of the final analyses. In case of deviations from the SAP, explanations will be provided in the Clinical Study Report (CSR).

██████ is contracted to support statistical analyses and is responsible for the production and quality control of all outputs described in this document.

## 2 Study Design

This is a phase 3 multinational, multicenter, prospective, randomized, double-blind, parallel-group, active and placebo-controlled study examining the effect of instillations of CUSA-081 versus placebo or alteplase in subjects with dysfunctional non-hemodialysis CVADs. Restoration of CVAD function is defined as follows: the ability to both withdraw at least 3 mL of blood and infuse 5 mL of saline.

Subjects will be screened according to the Study Inclusion and Exclusion criteria and will be candidates for randomization if all eligibility criteria are met.

A minimum of 841 subjects, within approximately 100 sites, will be randomized, in a 9:1:6 ratio of CUSA-081:Placebo:alteplase in order to achieve a minimum of 800 subjects completing the study:

Treatment Arm A (CUSA-081 [reteplase])	473 subjects
Treatment Arm B (Placebo)	53 subjects
Treatment Arm C (alteplase)	315 subjects

A total of 2-3 visits will be performed during the study, as follows (refer to the Study Treatment Schema in Figure 1 for more details):

[figure not shown]
- Screening (Baseline Visit) (Day 0 or Day 1).
- Treatment Visit 1 (V1) (Day 1):
  - Subjects will receive the first instillation of study drug (CUSA-081, placebo or alteplase) into the catheter via the single lumen designated for this study.
  - If patency is not restored after 90 minutes following the first instillation, a second dose of study drug (same drug as at first instillation) will be administered.
- Follow-up Visit 2 (V2) (Day 30 ± 2 days) (can be performed by telephone).

An extra visit could be performed as Screening (Baseline Visit) for logistical reasons. Day 1 must be the following calendar day (for example, Monday and Tuesday; not Friday and Monday). Informed consent will be signed during this visit.

Safety will be monitored throughout the study.

The end of the trial is defined as the last follow-up contact of the last subject to receive study drug in the trial.

**Figure 1: Treatment Schema**

A futility analysis is planned to occur when approximately 416 subjects have completed the study (see Section 7.5 for additional details).

The futility analysis will assess the conditional power for the test of non-inferiority of CUSA-081 compared to alteplase in the rate of treatment success following a single administration of study drug with a dwell time up to 90 minutes.

If the futility analysis finds that it is unlikely to demonstrate non-inferiority of CUSA-081 compared to alteplase, then the study will be terminated early.

A separate independent and unblinded team will be established to perform the futility analysis and prepare the data for review (“Unblinded Statistical/Programming Team”).

An independent and unblinded Data Monitoring Committee (DMC) will be established to review the data and provide a recommendation regarding the continuation of the study. Details of the DMC, including roles, responsibilities, communication processes, and frequency of meetings will be provided in a separate DMC Charter.

The DMC will provide a recommendation regarding the continuation as follows:

- the study should continue without modification;
- the study should be terminated prematurely.

The study team and the other blinded team members will remain blinded throughout the futility analysis.

### **Treatment Allocation**

A balanced block randomization scheme will be prepared via a computerized system. Once the subject meets all inclusion and no exclusion criteria and has provided informed consent, the investigational pharmacist or designee at the study site will enroll the subject and request the study drug assignment using the Interactive Response Technology (IRT) at the time of randomization. Randomization of study drug must only occur on the day of study drug administration.

Assignment to double-blind treatment arms will be determined by the randomization schedule programmed into the IRT. Once a subject is randomized, the study site unblinded Pharmacist will be provided a study drug kit allocation and the appropriate ancillary kit allocation via the IRT. The unblinded Pharmacist will prepare the study drug and affix a blinded label to the syringes for dispensation to the blinded site personnel for administration to the subject.

## **2.1 Study Schedule**

The study schedule (Table 1) summarizes the study assessments by visit and time point.

Due to the short nature of the treatment period and the ability for the follow up visit to be conducted via telephone, no missing data or modifications are anticipated due to COVID-19. Additionally, no modifications to study procedures or study drug administration are anticipated. In the event that a subject withdraws from the study due to COVID-19, this reason will be documented.

**Table 1: Study Schedule**

Assessment or Procedure	Screening and/or Treatment Visit  (Day 1) 									Visit 2 – Follow-Up Assessment 
	Screen Day 0 Or Day 1	Syringe 1 First Dose (at 0 min)				Syringe 2 Second Dose (at 90 min, if given)				Day 30 (±2 days) after Treatment 
		0 Min	30 Min	60 Min	90 Min	90 Min	120 Min	150 Min	180 Min	
Informed consent	X									
Inclusion/exclusion criteria	X									
Demographic data	X									
Medical history	X									
Body weight and height	X									
Blood pressure measurement and heart rate (HR)	X 									
Urine pregnancy test 	X									
Concomitant medications/procedures	X 									X 
CVAD history	X									
CVAD function assessment	X 		X 	X 	X 		X 	X 	X 	X 
Enrollment into IRT	X									
Study drug administration		X 				X 				
Adverse events	X 	X 	X 	X 	X 	X 	X 	X 	X 	X 
CVAD = central venous access device; d = day; IRT = interactive response technology, min = minutes.										

-  If at any time after the first instillation of study drug, a subject is withdrawn from the study (due to subject's wishes or at the Investigator's discretion), safety monitoring for that subject should still occur for up to 30 days ( $\pm 2$  days) after the last withdrawal of study drug from the catheter (see adverse event section [AE] collection period in protocol Section 10).
-  Subjects will be screened for eligibility and treated over the course of one or two study visits. Randomization only occurs on day of treatment and cannot occur on screening visit if not the same as the treatment day. Therefore, the Screening Visit may occur on Day 0 or Day 1 (for example Monday and Tuesday; not Friday and Monday) and the Treatment Visit will occur on Day 1. Screening assessments will occur prior to the first dose of study medication. Blood pressure, heart rate, CVAD assessment and all other eligibility for inclusion criteria must be reassessed if screening and treatment are conducted on separate days.
-  Subjects who are unable to be reached for follow-up assessment after discontinuing study drug will be categorized as lost to follow up from the study.
-  The Day 30 ( $\pm 2$  days) follow-up assessment will occur via phone or may occur in person if the subject has a scheduled clinic visit. The follow-up period is calculated from the date of the randomization/treatment day.
-  A urine pregnancy test is required for all females of childbearing potential. Women in natural or surgical post-menopause do not need to be tested for pregnancy.
-  Only concomitant medications and/or procedures ongoing at the time of consent, or stopped within 30 days prior to informed consent, and only new concomitant medications and/or procedures related to spontaneously reported SAEs/AESIs will be collected after randomization.
-  Note that all catheter assessments are based on the dwell time from the time of study drug instillation (i.e., from "0 min"; NOT from the time of the prior assessment). All efforts should be made to conduct the assessment at the required time point. The window of  $\pm 5$  minutes is also from the time of study drug instillation and not time of the prior assessment. Assessments of catheter dysfunction are described in Sections 7.1.1 and 7.2.3 of the protocol. In the event a 2nd dose of study drug is needed, it should be administered within 15 min of withdrawal of the 1st dose from the CVAD.
-  Once CVAD function has been restored (i.e. the ability to both withdraw at least 3 mL of blood and infuse 5 mL of saline solution), the subject will be deemed a Treatment Success and will exit the treatment algorithm (Figure 1). Therefore, subsequent dosing and catheter function checks will not be performed during V1. At 180 minutes, or in the case of Early Withdrawal, if treatment success is not achieved, any subsequently administered standard of care and related outcome will be documented.
-  Assessment of recurrent catheter dysfunction as described in Section 7.1.2 of the protocol. Information including, but not limited to, the need for other thrombolytic administration and/or catheter removal or replacement will be collected beyond study drug administration and up through Day 30 ( $\pm 2$  days). Subjects will be requested to document the date of re-occlusion and any intervention or the date the catheter was removed in order to provide the data when contacted by site personnel.
-  Collection of AEs and SAEs will begin from the time of Informed Consent signature. All AEs, TEAEs and SAEs on-going at the time the subject's study treatment ends should be evaluated up to 30 days after last administration of Study Drug. After this period, all unresolved TEAEs will be reported as "ongoing" in the CRF.

## 3 Study Objectives

### 3.1 Primary Objective

- To demonstrate the superiority of CUSA-081 compared to placebo in the rate of treatment success following a single administration with a dwell time up to 90 minutes. Treatment success is defined as restoration of CVAD functionality measured as the ability to withdraw 3 mL of blood and infuse 5 mL of saline.

### 3.2 Secondary Objectives

1. To demonstrate the non-inferiority of CUSA-081 compared to alteplase in the rate of treatment success following a single administration with a dwell time up to 90 minutes;
2. To demonstrate the superiority of CUSA-081 compared to placebo in the rate of treatment success following a single administration with a dwell time up to 60 minutes;
3. To demonstrate the superiority of CUSA-081 compared to placebo in the rate of treatment success following up to two administrations with a dwell time up to 180 minutes;
4. To demonstrate the superiority of CUSA-081 compared to alteplase in the rate of treatment success following a single administration with a dwell time up to 90 minutes;
5. To evaluate the safety and tolerability of CUSA-081;
6. To evaluate the rate of recurrent catheter dysfunction defined as first re-occlusion within 30 days following treatment with CUSA-081.

## 4 Study Variables

### 4.1 Efficacy Variables

#### 4.1.1 Primary Efficacy Variable

- The primary efficacy variable is the percentage of subjects who have treatment success following a single instillation of study drug (CUSA-081, alteplase, or placebo) with a dwell time up to 90 minutes. Treatment success is defined as the restoration of CVAD functionality measured as the ability to withdraw 3 mL of blood and infuse 5 mL of saline.

#### 4.1.2 Secondary Efficacy Variables

1. Percentage of subjects who have treatment success following a single instillation of study drug with a total dwell time up to 30 and 60 minutes;
2. Percentage of subjects who have treatment success after up to two instillations of study drug with a total dwell time up to 120, 150 and 180 minutes;
3. Rate of recurrent catheter dysfunction (defined as first re-occlusion) within 30 days following treatment with study drug.

### 4.2 Safety Variables

- Treatment Emergent Adverse Events (TEAE), Adverse Drug Reactions (ADRs), Serious Treatment Emergent Adverse Events (SAE), serious related TEAEs, TEAEs leading to study withdrawal, and TEAEs leading to death;
- Treatment Emergent Adverse Events of Special Interest (AESI) as defined in Section 10.1 of the protocol.

## 5 Sample Size

For the primary assessment of the superiority of CUSA-081 vs. placebo, a sample size of 450 in the active arm (CUSA-081), and 50 in the control arm (placebo), will provide >99% power to detect a difference of  $\geq 35\%$  using a two-sided test at significance level of 0.05. The expected placebo response rate is approximately 20%.

For the assessment of the non-inferiority of CUSA-081 vs alteplase, a sample size of 450 in the active arm (CUSA-081), and 300 in the control arm (alteplase) will provide 87% power at the 2.5% significance level (that is by using one-sided 97.5% confidence intervals (CI)) with a non-inferiority margin of -10%, assuming an equal response rate of 75% in the control arm (alteplase), and the active (CUSA-081) arm. A sample size of 450 in the active arm (CUSA-081), and 300 in the control arm (alteplase) will also provide 92% power to detect a difference of 10% between the success rates using a two-sided test at significance level of 0.05.

A minimum of 841 subjects will be randomized in order to achieve a minimum of 800 subjects completing the study.

## 5.1 Statistical Consideration of Non-Inferiority Margin

The selection of the non-inferiority margin was based upon the following reasoning. The non-inferiority margin must be less than the smallest treatment difference between standard therapy and placebo (M1), and at least part of the treatment effect of the standard therapy must be preserved for the test drug (M2).

The NI margin of -10% between reteplase vs. alteplase was selected based on the following statistical consideration:

M1 = the smallest treatment effect of alteplase over placebo

M2 = a fraction 50% of M1 is the most commonly used value

**Table 2:** Historical Placebo Response

Study / Time point		Number of responders / Sample size	% Response	Lower 95% CI	Upper 95% CI
TROPICS 1 ( Gabrail et al, 2010 )	120 minutes	11/47	23%	11%	36%
COOL 1 ( Cathflo PI, 2017 )	120 minutes	12/74	16%	8%	25%

Placebo responses in the treatment of thrombotically occluded CVADs have been reported in hemodialysis setting and in non-hemodialysis setting. We included the available placebo responses data from 2 studies in the non-hemodialysis setting (Table 2) with a definition of treatment success similar to the one used in this study and with a timepoint assessment of  $\geq 90$  minutes. Based on the data from these two studies, we estimated the placebo response using a weighted analysis based on a random effect model (DerSimonian-Laird). The weighted placebo response is 19% with 95% CI of 12.9% to 26.8%.

Based on the CATHFLO ACTIVASE product label, the restoration of catheter function was assessed at 30 and 120 minutes after the first instillation of alteplase. The response at 90 minutes was estimated based on linear interpolation.

Table 3 shows the observed response rates at 30 minutes and 120 minutes and the estimated 95% CI at 90 minutes.

**Table 3: Historical Alteplase Response**

Time point (COOL 2)		# of responders / Sample size	% Response	Lower 95% CI	Upper 95% CI
30 minutes	observed	516/995	51.9%	48.8%	55.0%
90 minutes	linear interpolation	670/995	67.3%	64.4%	70.3%
120 minutes	observed	747/995	75.1%	72.4%	77.8%

Based on the linear interpolation, the lower bound of the 95% CI of Alteplase response at 90 minutes is 64.4%. The upper bound of the 95% CI for the weighted placebo response is estimated to be 26.8%. Therefore, the alteplase margin over placebo is at least 37.6% at 90 minutes. To preserve 50% of M1 in a NI trial, a NI margin of 18.8% (half of 37.6%) would be reasonable.

A more conservative -10% NI margin between reteplase and alteplase will be used for the 90 minutes endpoint in this trial, which should preserve >70% of M1.

## 6 Analysis Sets

The definitions of the analysis sets are summarized below. A final agreement on the subjects to be included in or excluded from each analysis set will be reached during the blind review of the data before breaking the blind. Inclusions and exclusions from analysis sets will be fully documented in the Data Review Report.

### 6.1 Safety Set (SS)

All randomized subjects who receive at least one dose of study drug. Subjects discontinued after dosing will be part of the SS. Analyses based on the SS will be based on the actual treatment received. The SS will be the primary analysis set for all safety analyses.

### 6.2 Intention-to-Treat Analysis Set (ITT)

All randomized subjects regardless if they received treatment with study drug. The ITT Set will be based on the randomized treatment allocation. The ITT Set will be used for sensitivity analysis for the primary efficacy analyses.

### 6.3 Full Analysis Set (FAS)

All randomized subjects who receive at least one dose of study drug, and with at least one available evaluation of efficacy after baseline (i.e. at least one CVAD assessment after study

drug administration). Analyses using the FAS will be based on the treatment randomized. The FAS will be the primary analysis set for all efficacy analyses involving assessment of superiority.

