## 6.4 Per-Protocol Analysis Set (PPS)

All subjects from Safety Set without any important protocol deviations. Important protocol deviations are a subset of protocol deviations that may significantly impact the completeness, accuracy, and/or reliability of key study data or that may significantly affect a subject's rights, safety, or well-being. Important protocol deviations will be assigned in a blinded manner prior to database lock. The PPS will be used for sensitivity analysis for the primary efficacy analyses and the non-inferiority analyses.

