### 7.3 Handling of Missing Data

In general, except as described below, missing data will not be imputed.

The number of subjects with missing data will be presented under a “Missing” category. Unless otherwise stated, missing values will not be included in the denominator count when calculating percentages.

When quantitative variables are being summarized, only the non-missing values will be evaluated for calculating summary statistics.

Other critical missing data, if any, will be discussed during the blind review of the data. Decisions will be fully documented in the Data Review Report.

Treatment Success: Missing CVAD Assessment

By design, all subjects exit the treatment algorithm once patency is achieved and no further assessments of catheter clearance are performed. Subjects are considered a treatment success at the time point at which patency was achieved and also at all subsequent time points during the treatment period.
 
Otherwise, if missing data is observed for assessment of treatment success and patency was not achieved prior to the time point with missing data, then the subject will be considered as a failure (worst case scenario) at the time point with missing data. The summary statistics for treatment success will display the derived data, including imputation for any missing data observed prior to treatment success.

Medications: Missing/Incomplete Date

In case of missing or incomplete dates/times not directly allowing allocation to any category of medications, a worst-case allocation will be done according to the available parts of the start and the stop dates/times. The medications will be allocated to the first category allowed by the available data, according to the following order:
 

1. Concomitant medication;

2. Maintained medication;

3. Post-treatment medication;

4. Prior medication.

Procedures: Missing/Incomplete Date

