## 9.1 Primary Efficacy Variable

The primary efficacy variable is the percentage of subjects who have treatment success following a single instillation of study drug (CUSA-081, alteplase, or placebo) with a dwell time up to 90 minutes. Treatment success will be derived as mentioned in Section 7.3.

Protocol violations and any other intercurrent events will be ignored for analyses performed on the FAS, which target a treatment policy estimand. Subjects with important protocol deviations will be excluded from analyses based on the PPS.

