### Non-Inferiority Hypotheses

The hypotheses for the non-inferiority are as follows:

The null hypothesis H0:  $R_c - R_a \leq -10$   
The alternative hypothesis H1:  $R_c - R_a > -10$

Where Rc=Rate of success of CUSA-081  
Ra=Rate of success of alteplase

Assessment of non-inferiority will be based on the 95% confidence interval for the difference in the rate of treatment success between CUSA-081 vs alteplase following a single administration with a dwell time up to 90 minutes.

Non-inferiority will be demonstrated (or null hypothesis will be rejected) when the lower limit of the 95% confidence interval for the difference in rate of success is greater than -10% (See Section 14.1).

The number and percent of subjects with treatment success by treatment group and time point will be summarized. The rate difference and associated 95% Wald confidence intervals between CUSA-081 and placebo or alteplase will be estimated. The between treatment comparisons will be performed using a 2-sample z test for proportions.

For superiority hypotheses, the primary analysis will be the analysis performed on the FAS. Analyses will be repeated based on the ITT and PP Sets as sensitivity analyses. For non-inferiority hypotheses, the analysis based on the PP Set will be considered as the primary analysis.

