## 12 Changes in the Planned Analyses from Study Protocol

- The protocol Section 12.2 describes the FAS as “the primary analysis set for all efficacy analyses”. The first secondary objective is “to demonstrate the non-inferiority of CUSA-081 compared to alteplase in the rate of treatment success following a single administration with a dwell time up to 90 minutes”. The primary analysis corresponding to this objective, which is included within the hierarchical closed testing procedure, will be based on the Per-Protocol Set, since this approach is considered as more conservative as per Section 5.2.3 of ICH E9. The FAS will be the primary analysis set for all efficacy analyses involving assessment of superiority.
- The protocol Section 12.3.7 describes an interim futility analysis. Since the study has been terminated by the Sponsor prematurely for other reasons, the futility analysis will not be conducted. The analysis to be conducted following the premature closure of the study will be exactly the analysis which is planned for end of study. The database lock and unblinding will be conducted according to the relevant SOPs of the Sponsor and CRO and the analysis conducted will be considered as the final study analysis.
- The definition of the Per-Protocol Set has been modified to use Safety Set instead of ITT Set in order to include in the Per-Protocol Set only treated subjects.

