Table 14.1.11.1	Concomitant Medications (Full Analysis Set)	CMT002		Same as Table 14.1.9.1

Table Number	Table Title	Template Code	Notes	Footnotes/Source Listing Number
Table 14.1.11.2	Concomitant Medications (Safety Set)	CMT002		Same as Table 14.1.9.1
Table 14.2.1.1.1	Summary and Statistical Analysis of Proportion of Subjects with Treatment Success Up to 90 Minutes Following a Single Instillation of Study Drug (Full Analysis Set)	ANT007	
 
- Replace “Adjusted Mean” with “Proportion of Treatment Success (95% CI)” and “Adjusted Mean difference” with “Difference in Proportions (95% CI)”.
 
- Do not display Parameter column.
 
- Replace Study Day by Timepoint.
 
- Timepoints to be presented: 30, 60 and 90 mins.
 
- Add column for P-value for all the treatment comparison at all timepoints as last column.
 
- In the column Treatment and after all treatments listed, add the different comparisons: CUSA-081 vs Placebo, CUSA-081 vs Alteplase, Alteplase vs Placebo.
 
- Replace ‘n’ by ‘n Success’.
 
	
Source: Listing 16.2.6.1
 
Footnotes: [1] ‘n Success’ corresponds to the number of subjects with treatment success. [2] The 95% confidence intervals of proportions and difference of proportions are based on Wald method. [3] The p-value is based on a 2-sample Z test for proportions. [4] Percentages are based on the number of subjects in the treatment group.

Table 14.2.1.1.2 ***	SAS Output: Summary and Statistical Analysis of Proportion of Subjects with Treatment Success Up to 90 Minutes Following a Single Instillation of Study Drug (Full Analysis Set)		Raw SAS output	
Table 14.2.1.2	Summary and Sensitivity Analysis of Proportion of Subjects with Treatment Success Up to 90 Minutes Following a Single Instillation of Study Drug (Intention-to-Treat Set)	ANT007	
Same as Table 14.2.1.1.1
 
The randomized but non-treated subjects will be considered as non-responders.
	Same as Table 14.2.1.1.1
Table 14.2.1.3.1	Summary and Sensitivity Analysis of Proportion of Subjects with Treatment Success Up to 90 Minutes Following a Single Instillation of Study Drug (Per-Protocol Set)	ANT007	Same as Table 14.2.1.1.1	Same as Table 14.2.1.1.1

Table Number	Table Title	Template Code	Notes	Footnotes/Source Listing Number

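### The FAS leaves out dosed subjects who have no post-dose assessment, although the plan's own missing-data rule would count them as failures

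*SAP*

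**What the plan says.** SAP 6.3 sets two conditions for the FAS: "All randomized subjects who receive at least one dose of study drug, and with at least one available evaluation of efficacy after baseline". It adds that this means a CVAD assessment after dosing, and it gives the set its role: "The FAS will be the primary analysis set for all efficacy analyses involving assessment of superiority". Protocol 12.2 and the protocol outline define the FAS in the same way.

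For a missing assessment where patency was not reached earlier, SAP 7.3 says "then the subject will be considered as a failure (worst case scenario) at the time point with missing data". Protocol 12.3.2 applies that rule to the primary and key secondary analyses of treatment success. On intercurrent events, SAP 9.1 says that they and protocol violations "will be ignored for analyses performed on the FAS, which target a treatment policy estimand".

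The PPS has no assessment condition. SAP 6.4 defines it as "All subjects from Safety Set without any important protocol deviations", and SAP Section 12 records the change: "The definition of the Per-Protocol Set has been modified to use Safety Set instead of ITT Set". The reason given there is to keep only treated subjects. Under the non-inferiority hypotheses in SAP 9.1, "For non-inferiority hypotheses, the analysis based on the PP Set will be considered as the primary analysis". (SAP 6.4 still calls the PPS a sensitivity set for non-inferiority; Sections 9, 9.1 and 12 make it primary, and that reading is used here.)

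The ITT Set is a planned sensitivity set for the primary analysis. The note to its table (Table 14.2.1.2, SAP 16.1) says "The randomized but non-treated subjects will be considered as non-responders".

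**The concern.** The first efficacy check is 30 minutes after instillation. Protocol 4.4 allows withdrawal for reasons such as an adverse event or withdrawn consent, and these can arise before that check. Whether such a subject enters the primary superiority analysis then depends on something that happened after dosing. The exclusion is not needed to obtain an outcome, because 7.3 supplies one. It also fits poorly with an estimand that is meant to disregard intercurrent events.

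Two things are at stake. If early loss differs between arms, the FAS comparison is tilted towards the arm that loses more unassessed subjects. And two confirmatory tests in one hierarchy can treat the same person differently: a failure in the non-inferiority test on the PPS, and absent from the superiority tests on the FAS.

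**Working it through.** **The plan's own figures.** These reproduce with z = 1.96.
- Superiority over placebo, 55% against 20%, 450/50, pooled z test. SE under the null = √(0.515 × 0.485 × (1/450 + 1/50)) = 0.0745. SE under the alternative = √(0.55 × 0.45/450 + 0.20 × 0.80/50) = 0.0612. Power = Φ((0.35 − 1.96 × 0.0745)/0.0612) = 99.96% (stated: above 99%).
- Non-inferiority, 75% in both arms, 450/300, margin 10 points. SE = √(0.75 × 0.25 × (1/450 + 1/300)) = 0.0323. Power = Φ(0.10/0.0323 − 1.96) = 87.3% (stated: 87%).
- Superiority over alteplase, 450/300. The rates are not stated; 85% against 75% gives 92.2% (stated: 92%).

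**Set membership by definition.**

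| Subject | ITT | Safety | FAS | PPS (SAP 6.4) |
|---|---|---|---|---|
| Dosed, assessed, no important deviation | yes | yes | yes | yes |
| Dosed, assessed, important deviation | yes | yes | yes | no |
| Dosed, never assessed, no important deviation | yes | yes | **no** | **yes** |
| Dosed, never assessed, important deviation | yes | yes | no | no |
| Never dosed | yes | no | no | no |

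The third row shows that the definitions do not make the PPS a subset of the FAS. Take withdrawal at minute 20: there is no assessment, so the subject leaves the FAS. Take withdrawal at minute 40 after an unsuccessful 30-minute check: the subject stays in the FAS and is a failure at 60 and 90 minutes under 7.3. Neither has a 90-minute observation.

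**Effect on the comparison with placebo.** Inputs are 473 and 53 subjects, and 55% and 20% success among those assessed. The fractions unassessed, m, are an assumption of 0-5% per arm. Keeping these subjects as failures gives a difference of 0.55(1 − m for CUSA-081) − 0.20(1 − m for placebo):
- none unassessed: 35.0 points, which is also the FAS value in every scenario;
- 2% in both arms: 0.539 − 0.196 = 34.3;
- 5% in both: 0.5225 − 0.190 = 33.3;
- 5% in CUSA-081 only: 0.5225 − 0.200 = 32.3;
- 5% in placebo only: 0.550 − 0.190 = 36.0.

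Power stays at or above 99.8% throughout. As an extreme, put all 841 − 800 = 41 allowed non-completers in CUSA-081, dosed and unassessed. The FAS rate is 238/432 = 55.1%; as failures they make it 238/473 = 50.3%. Against 11/53 = 20.8% on placebo the difference is 29.6 points and z = 4.09.

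**Direction.** Dropping unassessed placebo subjects raises the placebo rate. With 10 successes, 10/53 = 18.9% becomes 10/52 = 19.2%, 10/51 = 19.6% or 10/50 = 20.0%. That narrows the difference and is conservative. The harmful direction is loss from CUSA-081.

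**Superiority over alteplase (secondary objective 4, last in the sequence).** Suppose both true rates are 75% with missing counted as failure, 473 against 315, and a fraction m is dropped from CUSA-081 only. The FAS rate for CUSA-081 is then 0.75/(1 − m), and d is its excess over 0.75. The chance of a significant result favouring CUSA-081 is 1 − Φ((1.96 × SE0 − d)/SE1), where SE0 is pooled and SE1 unpooled.
- m = 0: 2.5%.
- m = 1% (0.01 × 473, about 5 subjects): d = 0.0076, SE0 = 0.0314, SE1 = 0.0314, giving 4.3%.
- m = 2% (about 9 subjects): d = 0.0153, SE0 = 0.0312, SE1 = 0.0313, giving 7.2%.
- 2% in both arms: d = 0, giving 2.5%.

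These are chances for that test taken alone; the earlier steps must also be passed.

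**The case against.** The strongest reply is that the plan already contains the analysis wanted. The ITT Set keeps every randomised subject, 7.3 makes the unassessed ones failures, and the table note does the same for those never dosed. Set sizes are tabulated by arm and exclusions are listed. The FAS definition comes from the protocol, and changing it departs from the protocol. The first check falls 30 minutes into a single visit, so few subjects can be affected; the 41-subject allowance covers non-completion up to Day 30 and is a generous ceiling. All of this stands, and it is why the point is minor. But a sensitivity analysis shows the effect without deciding the confirmatory test.

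Three stronger readings are tempting and are not supported.
- A reader might infer that the non-inferiority conclusion is compromised by the FAS rule. The primary non-inferiority analysis is on the PPS; a FAS result would be supportive only.
- A reader might infer that known non-responders are being removed. Their outcome was never observed; they are failures only by the plan's imputation rule.
- A reader might infer that the PPS will in fact fall outside the FAS. That needs such a subject to exist and blinded review not to class the case as an important deviation. SAP 6.4 includes deviations that affect completeness of key data, so review could remove the subject from both sets.

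Likewise, a 5% loss from CUSA-081 alone would put the false-win chance at about 25%, but nothing in the documents suggests a loss of that size or one confined to one arm.

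**Conclusion.** The point holds as a minor inconsistency in a confirmatory definition. The FAS condition excludes subjects for a post-dose reason, while 7.3 already assigns their outcome and 9.1 claims a treatment policy estimand. The PPS, as now defined, can treat the same subject the other way.

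The primary test against placebo is robust at planned size: 32.3 to 36.0 points against 35.0 under an assumed 0-5% unassessed per arm. The exposed test is superiority over alteplase, where a loss of 1% or 2% confined to CUSA-081 would raise the false-win chance from 2.5% to 4.3% or 7.2%; equal loss leaves it at 2.5%. The loss fractions are assumptions, since the documents give no count of dosed, unassessed subjects. SAP Section 12 records that the sponsor ended the study early and the documents give no final number, so these results apply to the planned size; in a smaller trial each subject weighs more.

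**What to change.** Before unblinding:
1. In SAP 6.3, define the FAS as everyone randomised and given one or more doses, analysed as randomised, and delete the condition on a post-dose evaluation. State that a dosed subject with no post-dose assessment is a failure under 7.3.
2. Make the same deletion in the FAS footnote of Table 14.1.1.7.
3. State in SAP 6.4 that the PPS is a subset of the FAS. With the first change this follows, because both sets then start from the randomised, dosed subjects. Correct the PPS footnote of Table 14.1.1.7, which still starts from the ITT Set.
4. Record the departure from protocol 12.2 in SAP Section 12.

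No new data are needed. The cost is a change from the protocol-defined FAS and possibly slightly lower success rates. Randomised subjects who were never dosed would still be outside the FAS; the ITT sensitivity analysis continues to cover them.
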